12.5.2 Secondary Efficacy

The secondary efficacy endpoints will be:

- Dichotomized IGA score at Week 4 where treatment success is defined as achieving clear to almost clear (i.e., a score of 0 or 1) and at least a 2-grade improvement in the IGA. These data will be analyzed using the CMH test stratified by analysis center.
- The percentage of subjects with EASI 75 (at least a 75% reduction) at Week 6 where the EASI score is defined as a composite score based on the evaluated severity of 4 key signs of AD (i.e., erythema, infiltration/papulation, excoriation, and lichenification), and the extent of disease in each of the 4 body regions (i.e., head/neck, trunk, upper limbs, and lower limbs) will be analyzed using the CMH test stratified by analysis center.
- The percentage of subjects with EASI 75 (at least 75% reduction) at Week 4 will be analyzed using the CMH test stratified by analysis center.
- Dichotomized IGA score at Week 10 where treatment success is defined as achieving clear to almost clear (i.e., score of 0 or 1) and at least a 2-grade improvement in the IGA from Baseline. These data will be analyzed using the CMH test stratified by analysis center.
- The percentage of subjects with EASI 75 (at least 75% reduction) at Week 10 will be analyzed using the CMH test stratified by analysis center.
- Percentage of subjects with score of "None" or "Mild" and at least a one-grade improvement from Baseline in the severity of pruritus at Week 2
- Percentage of subjects with score of "None" or "Mild" and at least a one-grade improvement from Baseline in the severity of pruritus at Week 1Dichotomized IGA score at Week 2 where treatment success is defined as achieving clear to almost clear (i.e., score of 0 or 1) and at least a 2-grade improvement in the IGA from Baseline. These data will be analyzed using the CMH test stratified by analysis center.

Evaluation of the secondary efficacy variables will use a gated sequential procedure starting with the comparisons of the first bulleted item and proceeding onto the next item. The process will terminate if a nonstatistically significant value is observed.

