The primary method of handling missing efficacy data will be the method of Markov Chain Monte Carlo multiple imputation. As a sensitivity analysis, the last observation carried forward method will be used (ie, the last available on-therapy observation for a subject will be used to estimate subsequent missing data points). Additionally, a tipping point analysis will be performed for the primary endpoint. No imputations will be made for missing safety data.

A statistical analysis plan (SAP), describing all statistical analyses will be provided as a separate document. The SAP will be finalized prior to unblinding of the study treatments.

Primary efficacy analysis: The primary efficacy endpoint will be used to compare twice daily application of IDP-124 Lotion and Vehicle Lotion. The percentage of subjects with treatment success at Week 6 will be analyzed using Cochran-Mantel-Haenszel (CMH) test stratified by analysis center.

Secondary efficacy analysis: Comparisons of secondary endpoints, will be performed using CMH tests stratified by analysis center. Evaluation of the secondary efficacy variables will use a gated sequential procedure starting with the comparisons in the predefined order as listed above. The process will terminate if a nonstatistically significant value is observed.

Tertiary efficacy analysis: For tertiary efficacy endpoints, all but the mean percent change from Baseline in the affected TBSA will be analyzed with the CMH test stratified by analysis center. The analysis of TBSA will use an Analysis of Covariance with factors of treatment and analysis center and a covariate of the Baseline TBSA score. Analyses of tertiary endpoints will be performed without adjusting for multiplicity.

Efficacy analyses will be performed using the intent-to-treat (ITT) population, the Week 6 per protocol (PP) population, and the Week 10 PP population. The ITT analysis set will be considered primary for the evaluation of efficacy. Safety analyses will be performed using the safety population.

All subjects who are randomized and dispensed study drug will be included in the ITT population.

All subjects who are randomized and receive at least 1 confirmed dose of study drug will be included in the safety population.

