11.3.5 Pregnancy

All pre-menses females (9 and older) and female subjects of childbearing potential must use an effective method of birth control during the course of the study, in a manner such that risk of contraceptive failure is minimized. Abstinence is allowed as a birth control method.

Before enrolling a female subject of childbearing potential in this clinical study, the investigator must review the following information about study participation:

- Informed consent/assent requirements.
- Contraceptives in current use.

Following review of this information and appropriate counseling for the subject and their parent/legal guardian, the investigator or designee and the subject and parent/legal guardian must sign the assent/informed consent before study enrollment.

During the study, all pre-menses females (9 and older) and female subjects of childbearing potential should be instructed to contact the investigator immediately if they suspect they might be pregnant (e.g., missed or late menstrual period).

If a subject or investigator suspects that the subject may be pregnant prior to study enrollment, the study drug must be withheld until the results of laboratory pregnancy testing are available. If pregnancy is confirmed, the subject must not receive study drug and must not be enrolled in the study. If pregnancy is suspected while the subject is receiving study treatment, the study drug must immediately be withheld until the result of pregnancy testing is known. If pregnancy is confirmed, the study drug will be permanently discontinued and the subject will be followed until the pregnancy comes to term. A Pregnancy Report form will be submitted to the sponsor, initially within 24 hours of the investigator's awareness and at the end of the pregnancy, which includes the outcome of the pregnancy and any complications occurring during the pregnancy or the delivery. If a pregnancy is associated with an SAE, and SAE report form and the pregnancy report form should be submitted to the sponsor within 24 hours of the investigators awareness.

12 Statistics

All statistical processing will be performed using SAS® unless otherwise stated. No interim analyses are planned. Except where noted, all statistical tests will be two-sided and will be performed at the 0.05 level of significance.

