12.5.1 Primary Efficacy

The primary efficacy endpoint will be used to compare twice daily application of IDP-124 Lotion and Vehicle Lotion.

The percentage of subjects with treatment success at Week 6 will be analyzed using CMH test stratified by analysis center.

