12.5.3 Tertiary Efficacy

The following tertiary efficacy endpoints will be analyzed to further characterize the treatment effect of IDP-124 Lotion over the Vehicle Lotion.

- Percentage of subjects with at least a "2-grade improvement" (based on bandings as defined in the POEM scale) from Baseline in the POEM score at Week 6 completed by the subject or parent/legal guardian (if applicable) prior to being seen by the investigator or study staff.
- Percentage of subjects with score of "None" or "Mild" and at least a one-grade improvement from Baseline in the severity of Sleep Disturbance at Weeks 1, 2, 4, 6 and 10 Overall sleep disturbance in the 24 hours prior to the visit as assessed by the subject and parent/legal guardian (if applicable).

- Percentage of subjects with score of "None" or "Mild" and at least a one-grade improvement from Baseline in the severity of pruritus at Weeks 4, 6 and 10 Overall pruritus in the 24 hours prior to the visit as assessed by the subject and parent/legal guardian (if applicable).
- Percentage of subjects with at least a 2-grade improvement from Baseline in the Subjects assessment score at Weeks 1, 2, 4, 6, and 10 Overall AD disease control over the 7 days prior to the visit as assessed by the subject and parent/ guardian using a score of 0 (complete disease control) to 3 (uncontrolled disease).
- Percentage of subjects with at least a 2-grade improvement from Baseline in the other signs and symptoms of AD at Weeks 1, 2, 4, 6 and 10 Investigators assessment at each visit for hyperpigmentation, hypopigmentation, and dry skin.
- Mean percent change from Baseline in the affected TBSA at each study visit.

All but the mean percent change from Baseline in the affected TBSA will be analyzed with the CMH test stratified by analysis center. The analysis of TBSA will use Analysis of Covariance with factors of treatment and analysis center and a covariate of the baseline TBSA score. Analyses of tertiary endpoints will be performed without adjusting for multiplicity.

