12.8.5 Multiplicity Issues

Not applicable.

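### The secondary testing sequence is not made conditional on the Week 6 primary, and Section 12.8.5 treats multiplicity as not arising, so error across primary and secondary claims is not held at 5%

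*Combined protocol and SAP*

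**What the plan says.** The primary test is in Section 12.5.1: "The percentage of subjects with treatment success at Week 6 will be analyzed using CMH test stratified by analysis center". That section does not link it to the secondary tests.

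The opening of Section 12 sets the default level: "Except where noted, all statistical tests will be two-sided and will be performed at the 0.05 level of significance".

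Section 12.5.2 lists the secondary endpoints, beginning with IGA success at Week 4, and tests them by a "gated sequential procedure starting with the comparisons of the first bulleted item and proceeding onto the next item". The stopping rule is "The process will terminate if a nonstatistically significant value is observed". The primary is not on that list.

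The synopsis describes the same procedure: "Evaluation of the secondary efficacy variables will use a gated sequential procedure starting with the comparisons in the predefined order as listed above". The order it points to is the list of secondary variables.

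Section 12.5.3 deals with the third tier openly: "Analyses of tertiary endpoints will be performed without adjusting for multiplicity". The whole of Section 12.8.5, Multiplicity Issues, is "Not applicable".

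**The concern.** A fixed sequence controls error only over the tests that belong to it. Here it begins at a secondary endpoint and the primary stands outside it. Two families, each at 5%, can then produce confirmatory claims independently of each other. If Week 6 IGA success is not significant, nothing in the protocol text stops a significant Week 4 IGA or EASI 75 result from being presented as a controlled finding.

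Section 12.8.5 adds an internal conflict. A gated procedure is a multiplicity procedure, and declaring only the tertiary endpoints unadjusted implies that the secondaries are meant to be controlled. The section where the rule belongs says that there is nothing to state.

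The primary test, its error rate and its power are not at issue. The exposure is in the secondary claims.

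**Working it through.** **Inputs from the protocol**

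- Two-sided 0.05 for each test (opening of Section 12), so the critical value is 1.96.
- Secondary sequence starting at Week 4 IGA and stopping at the first non-significant result (Section 12.5.2).
- No interim analyses (Section 12.7), so no other use of alpha.
- Planning rates of 23.6% and 6.3%, 232 and 116 subjects, Fisher's exact test, power above 95% (Section 12.8.2).

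**Assumed input.** The correlation r between the Week 6 and Week 4 test statistics is not given, so a range is shown.

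**1. The plan's own power figure**

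- Pooled rate: (232 × 0.236 + 116 × 0.063) / 348 = 0.1783.
- Null standard error: √[0.1783 × 0.8217 × (1/232 + 1/116)] = 0.0435.
- Alternative standard error: √[0.236 × 0.764/232 + 0.063 × 0.937/116] = 0.0359.
- Power: Φ[(0.173 − 1.96 × 0.0435) / 0.0359] = 99.3%.
- Full enumeration of the two-sided Fisher test gives 99.27%.

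Both agree with the stated figure of more than 95%.

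**2. Why two tests are the relevant count.** In a fixed sequence, a false positive requires rejecting the first truly null secondary that is reached, which is tested once at 5%. The eight secondaries therefore add at most one 5% error to that of the primary. The ceiling is 0.05 + 0.05 = 10%. At independence the figure is 1 − 0.95² = 9.75%.

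**3. Error as written.** Let Z1 (Week 6) and Z2 (Week 4) be standard bivariate normal with correlation r, both truly null.

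- A: any false positive = 1 − P(|Z1| ≤ 1.96 and |Z2| ≤ 1.96).
- B: any false positive favouring the lotion = 1 − P(Z1 ≤ 1.96 and Z2 ≤ 1.96). The nominal value is 2.5%.
- C: false Week 4 claim for the lotion without a primary win = B − 2.5%.

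| r | A | B | C |
|---|---|---|---|
| 0 | 9.75% | 4.94% | 2.44% |
| 0.3 | 9.51% | 4.76% | 2.26% |
| 0.5 | 9.07% | 4.54% | 2.04% |
| 0.7 | 8.35% | 4.17% | 1.67% |
| 0.8 | 7.81% | 3.90% | 1.40% |
| 0.9 | 7.04% | 3.52% | 1.02% |
| 0.95 | 6.46% | 3.23% | 0.73% |

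Low correlations are not expected, because the two tests use the same responder definition in the same subjects two weeks apart.

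A simulation of 1,000,000 draws gave 9.06%, 8.38% and 7.02% for A at r = 0.5, 0.7 and 0.9. The secondary family alone stayed at 5.0% in each case.

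**4. Error with a primary-first gate.** If the primary is truly null, no secondary can be claimed unless the primary has already been falsely rejected, so the error is that of the primary: 4.98% to 5.03% in the simulation. If the primary effect is real, the fixed sequence limits false secondary claims to 5%.

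**The case against.** The strongest reply is that this is silence rather than a wrong rule. The protocol names one primary variable and an ordered list of secondaries tested by a gated procedure, and primary-first is a natural reading of that structure. It nowhere expressly permits a secondary claim after a failed primary. The separate SAP, due before unblinding, may state the condition. This stands as a limit: the finding covers the protocol text, and does not show that the trial will be analysed without control. It does not remove the point, because Section 12.5.2 names an explicit starting place that is not the primary, and a SAP rule would still have to be reconciled with Section 12.8.5.

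Second, the 7% to 9% counts results favouring vehicle, which could support no claim for the lotion. That is fair: column C, 1.0% to 2.0% for r from 0.9 to 0.5, measures the practical harm better.

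Third, the inflation needs the Week 6 primary to be truly null, and on the planning rates a failed primary would be rare. Both are correct, but error control is meant for the case where the planning rates are wrong.

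Fourth, with two arms, one primary and no interim analysis, Section 12.8.5 can be read as saying only that the primary needs no adjustment. That reading is possible, but it leaves the secondary gate unmentioned in the section on multiplicity.

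**Conclusion.** The point holds for the protocol text and should be fixed. Each family is held at two-sided 5%, but the two together are not. If both endpoints are null, the joint two-sided error is 9.1% at r = 0.5 and 7.0% at r = 0.9, falls to 6.5% at r = 0.95, and cannot exceed 10%. In favour of the lotion alone it is 4.5% to 3.5% over r from 0.5 to 0.9, against 2.5%.

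These figures assume the correlations shown and tests of exact nominal size; the plan's own test is a CMH statistic transformed and combined over imputed data sets. They also assume that the secondaries form a strict order. The last bullet runs Week 1 pruritus and Week 2 IGA together, which may be only a lost line break in the extracted text.

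**What to change.** In Section 12.5.2 and the synopsis, state a rule of this kind:

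> The secondary endpoints are tested in the listed order, each at two-sided 0.05, only if the Week 6 primary is significant at two-sided 0.05 in favour of IDP-124 Lotion, and each only if every earlier secondary is also significant in that direction.

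Replace the entry in Section 12.8.5 with the same rule and carry it into the SAP before unblinding. If Week 1 pruritus and Week 2 IGA share a bullet in the source document, list them as two ordered steps.

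The cost is two or three sentences. Sample size and primary power do not change. The one downside is that no confirmatory secondary claim is possible if the primary fails. At the planning rates that would happen in about 100% − 99.27% = 0.7% of trials. That figure rests on Fisher's test and planning rates derived with LOCF, whereas the analysis will use CMH tests with multiple imputation.

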12.5.3 Tertiary Efficacy

The following tertiary efficacy endpoints will be analyzed to further characterize the treatment effect of IDP-124 Lotion over the Vehicle Lotion.

- Percentage of subjects with at least a "2-grade improvement" (based on bandings as defined in the POEM scale) from Baseline in the POEM score at Week 6 completed by the subject or parent/legal guardian (if applicable) prior to being seen by the investigator or study staff.
- Percentage of subjects with score of "None" or "Mild" and at least a one-grade improvement from Baseline in the severity of Sleep Disturbance at Weeks 1, 2, 4, 6 and 10 Overall sleep disturbance in the 24 hours prior to the visit as assessed by the subject and parent/legal guardian (if applicable).

- Percentage of subjects with score of "None" or "Mild" and at least a one-grade improvement from Baseline in the severity of pruritus at Weeks 4, 6 and 10 Overall pruritus in the 24 hours prior to the visit as assessed by the subject and parent/legal guardian (if applicable).
- Percentage of subjects with at least a 2-grade improvement from Baseline in the Subjects assessment score at Weeks 1, 2, 4, 6, and 10 Overall AD disease control over the 7 days prior to the visit as assessed by the subject and parent/ guardian using a score of 0 (complete disease control) to 3 (uncontrolled disease).
- Percentage of subjects with at least a 2-grade improvement from Baseline in the other signs and symptoms of AD at Weeks 1, 2, 4, 6 and 10 Investigators assessment at each visit for hyperpigmentation, hypopigmentation, and dry skin.
- Mean percent change from Baseline in the affected TBSA at each study visit.

All but the mean percent change from Baseline in the affected TBSA will be analyzed with the CMH test stratified by analysis center. The analysis of TBSA will use Analysis of Covariance with factors of treatment and analysis center and a covariate of the baseline TBSA score. Analyses of tertiary endpoints will be performed without adjusting for multiplicity.

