MCMC	Markov Chain Monte Carlo
MedDRA	Medical Dictionary for Regulatory Activities
POEM	Patient-Oriented Eczema Measure
PP	per protocol
SAE	serious adverse event
SAP	statistical analysis plan
TBSA	total body surface area
TEAE	treatment-emergent adverse event
US	United States
UV	ultraviolet

5 Introduction

Atopic dermatitis (AD) is a very common chronic dermatosis with a prevalence of 10% to 20% in children and 1% to 3% in adults [1]; AD poses difficult therapeutic challenges and may have a profound effect on a patient's quality of life. The disease gives rise to itching and severely dry skin, and is characterized by an allergic predisposition, pruritus, erythema, oozing, crusting, excoriations, lichenification, sensitivity to allergens/irritants, and a susceptibility to secondary infections [2, 3].

Reactive treatment with topical corticosteroids is the classical paradigm of care, but while these compounds are effective, they are restricted in long-term use by local and systemic side effects. Specifically, the use of topical corticosteroids is associated with potential local and systemic side effects including skin atrophy, telangiectasia, dyspigmentation, suppression of the hypothalamic-pituitary-adrenal axis and the rebound effect. Aside from corticosteroids, there is only a limited armament of topical treatments available for AD, most of which have certain side effects that limit their use.

Ascomycin derivatives, such as pimecrolimus, represent a class of anti-inflammatory macrolactams that inhibit the phosphatase calcineurin [4-6]. Studies on the effect of ascomycin derivatives and other immunophilin ligands in animal models of skin inflammation provided evidence that they are effective in the treatment of skin diseases in humans such as chronic plaque psoriasis, without the well-known side effects of topical corticosteroids [7, 8]. Intensive studies on structure-activity relationships and comparative pharmacological evaluations resulted in the discovery and development of pimecrolimus [9, 10]. Pimecrolimus selectively acts on cells involved in skin inflammation, targeting T cells and mast cells, and inhibiting the production and release of proinflammatory cytokines.

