11.2.2 Investigators Global Assessment

At Screening, Day 1 (Baseline), Week 1, 2, 4, 6 and 10 study visits (all visits), AD severity will be determined by the investigator/evaluator based on a global assessment of the inflammatory signs of AD. Evaluations will be graded on a static scale ranging from 0 (clear) to 4 (severe) as shown in the following table:

Score	Grade	Description	
0	Clear	No inflammatory signs of AD (no erythema, no induration/papulation, no lichenification, no oozing/crusting). Post-inflammatory hyperpigmentation and/or hypopigmentation may be present.	
1	Almost clear	Barely perceptible erythema, barely perceptible induration/papulation, and/or minimal lichenification. No oozing or crusting.	
2	Mild	Slight but definite erythema (pink), slight but definite induration/papulation, and/or slight but definite lichenification. No oozing or crusting.	
3	Moderate	Clearly perceptible erythema (dull red), clearly perceptible induration/papulation, and/or clearly perceptible lichenification. Oozing and crusting may be present.	
4	Severe	Marked erythema (deep or bright red), marked induration/papulation, and/or marked lichenification. Disease is wide-spread in extent. Oozing or crusting may be present.	

The primary efficacy variable is the IGA score at Week 6. Treatment success is defined as achieving clear to almost clear (i.e., a score of 0 or 1) and at least a 2-grade improvement in the IGA score at the end of treatment compared with Baseline.

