11.2.5 Other Signs and Symptoms of AD

Other signs and symptoms of AD to be assessed by the investigator will include hyperpigmentation, hypopigmentation, and dry skin. These assessments will be performed at Baseline, and Weeks 1, 2, 4, 6, and 10. The scales used for assessing these signs and symptoms are as follows:

Score	Grade	Description		
Hypopigmentation				
0	None	No evidence		
1	Mild	Slight, barely perceptible		
2	Moderate	Definite, evident		
3	Severe	Marked, prominent		
Hyperp	pigmentation			
0	None	No evidence		
1	Mild	Slight, barely perceptible		
2	Moderate	Definite, evident		
3	Severe	Marked, prominent		
Dry Sk	Dry Skin			
0	None	No dryness		
1	Mild	Slight, but definite roughness		
2	Moderate	Definite roughness		
3	Severe	Marked roughness		

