11.3.4 Adverse Events

An AE is any untoward medical occurrence in a subject or clinical investigation subject administered a medicinal product and which does not necessarily have a causal relationship with the study drug. Thus, AEs include any unfavorable and unintended illness, sign, symptom, clinically significant laboratory test abnormality, or disease temporally associated with the use of a medicinal product that has appeared or worsened during the course of the clinical study, regardless of causal relationship to the study drug(s) under study. The collection of non-serious AEs and serious AEs (SAEs) should begin following the subject's completion of the consent/assent process to participate in the study.

Descriptions of AEs will include the dates of onset and resolution, maximum severity, seriousness, action taken regarding study drug, corrective treatment, outcome, and investigator's assessment of causality. Worsening of disease will not be considered an AE unless it results in discontinuation of the subject from the study or requires medical intervention prohibited by the protocol. All AEs will be followed to resolution or until stable as determined by the investigator.

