Descriptive statistics will be used to provide an overview of the efficacy and safety results. For categorical parameters, the number and percentage of subjects in each category will be presented. For continuous parameters, descriptive statistics will include n (number of subjects), mean, standard deviation, median, minimum, and maximum. Appropriate inferential statistics will be used for the primary, secondary, and tertiary efficacy variables.

The primary method of handling missing efficacy data will be the method of Markov Chain Monte Carlo (MCMC) multiple imputation. As a sensitivity analysis, the last observation carried forward method (LOCF) will be used (i.e., the last available on-therapy observation for a subject will be used to estimate subsequent missing data points). Additionally, a tipping point analysis will be performed for the primary endpoint. No imputations will be made for missing safety data.

A statistical analysis plan (SAP), describing all statistical analyses will be provided as a separate document. The SAP will be finalized prior to unblinding of the study treatments.

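### Pigmentation and dry-skin grades have only an improvement analysis named, so worsening that meets no AE trigger has no planned subject-level tabulation by arm

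*Combined protocol and SAP*

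**What the plan says.** Section 11.2.5 sets up the scales: "Other signs and symptoms of AD to be assessed by the investigator will include hyperpigmentation, hypopigmentation, and dry skin". Each runs from 0 (none) to 3 (severe). The timing is fixed in the same section: "These assessments will be performed at Baseline, and Weeks 1, 2, 4, 6, and 10".

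Section 12.5.3, like the Synopsis, names one analysis for these grades, "Percentage of subjects with at least a 2-grade improvement from Baseline in the other signs and symptoms of AD", tested by CMH stratified by analysis center. On multiplicity it adds: "Analyses of tertiary endpoints will be performed without adjusting for multiplicity".

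Section 12.6 (Safety) covers adverse events, laboratory tests, vital signs and concomitant medications. Section 12.6.2 plans shift tables for laboratory values only. None of the three skin scales appears in Section 12.6, although tolerability is one of the objectives in Section 6.

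Two AE rules bear on these signs. Section 11.3.4 says "Worsening of disease will not be considered an AE unless it results in discontinuation of the subject from the study", and adds a second exception for worsening that needs an intervention the protocol prohibits. Section 11.3.4.3 makes cutaneous tolerability signs an AE when they lead to a concomitant therapy or to discontinuation.

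The opening of Section 12 has a general rule for efficacy and safety results: "For categorical parameters, the number and percentage of subjects in each category will be presented".

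**The concern.** A responder rate for improvement answers one question: did existing pigment change or dryness resolve? It does not say whether these signs appeared or got worse on the new lotion. Because the protocol classes them as signs of AD, a site may treat their worsening as disease worsening under Section 11.3.4 and record no AE.

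The other efficacy scales do not fill the gap. The Clear grade of the IGA states that "Post-inflammatory hyperpigmentation and/or hypopigmentation may be present". The four EASI signs in Section 11.2.3 include neither dryness nor pigmentation, and its area score leaves dry skin out.

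At stake is the support for a statement on local tolerability. Section 5 lists, for topical corticosteroids, "potential local and systemic side effects including skin atrophy, telangiectasia, dyspigmentation" and presents ascomycin derivatives as lacking those effects. A favourable statement about the lotion needs an output that could contradict it. The blinded, vehicle-controlled grades that could do so are already collected.

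**Working it through.** **Plan's own figures.** The plan gives no rate, power or precision for these three signs. Its only power statement is for the primary IGA endpoint (Section 12.8.2: 23.6% versus 6.3%, 232 versus 116 subjects, Fisher's exact test, two-sided 0.05, power above 95%). Full enumeration gives 99.3%, so that statement reproduces. It is not affected by this point.

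**Step 1: what the named endpoint can register.** Four Baseline grades by four visit grades give 16 pairs:

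| Change | Pairs | Number | Coded as |
|---|---|---|---|
| Improved by 2 or more | 2→0, 3→0, 3→1 | 3 | success |
| Improved by 1 | 1→0, 2→1, 3→2 | 3 | failure |
| Unchanged | 0→0, 1→1, 2→2, 3→3 | 4 | failure |
| Worsened | 0→1, 0→2, 0→3, 1→2, 1→3, 2→3 | 6 | failure |

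All 6 worsening pairs share a code with no change. Five of the six start from grade 0 or 1, from which success is impossible. A lower success rate on lotion would not separate less improvement from more worsening.

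**Step 2: what the AE rules require.** Take a subject whose hypopigmentation goes from 0 to 2, who is not treated for it and who stays in the study. Neither exception in Section 11.3.4 applies, and the trigger in Section 11.3.4.3 is not met. Now take new dryness managed with a permitted bland emollient (Sections 9.4.2 and 10.1.3). That is not an intervention the protocol prohibits, so the Section 11.3.4 exception does not apply. It arguably is a concomitant therapy under Section 11.3.4.3, because Section 11.1.2 has sites review emollients together with concomitant therapies. Two sites could record the same event differently.

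**Step 3: what marginal grade counts would show.** All rates here are assumptions. Baseline grades 0/1/2/3 are 50/25/20/5% in both arms. Of subjects at grades 0 to 2, 15% on lotion and 5% on vehicle worsen by one grade. Of subjects at grades 1 to 3, 40% on lotion and 25% on vehicle improve by one grade.

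- Grade 0 at the visit, lotion: 0.50×0.85 + 0.25×0.40 = 0.525. Vehicle: 0.50×0.95 + 0.25×0.25 = 0.5375.
- Grade 3 at the visit, lotion: 0.05×0.60 + 0.20×0.15 = 0.060. Vehicle: 0.05×0.75 + 0.20×0.05 = 0.0475.
- Any grade above 0: 47.5% versus 46.25%, a gap of 1.25 points.
- Worsened: 0.95×0.15 = 14.25% versus 0.95×0.05 = 4.75%, a gap of 9.5 points.

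If improvement is equal in the two arms, at any rate, the improvement terms cancel and the any-grade gap is 0.50×(0.95 − 0.85) = 5.0 points. The marginals therefore dilute the worsening difference, by an amount that depends on how improvement differs. In this example the planned endpoint is 0% in both arms by construction, since only one-grade improvement is allowed, so that zero is not evidence.

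**Step 4: what a direct worsening comparison could detect.** Exact two-sided Fisher power at 0.05 for 232 versus 116 subjects, rates assumed:

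| Lotion | Vehicle | Expected subjects | Power |
|---|---|---|---|
| 5% | 2% | 11.6 v 2.3 | 20% |
| 10% | 2% | 23.2 v 2.3 | 83% |
| 10% | 5% | 23.2 v 5.8 | 31% |
| 15% | 5% | 34.8 v 5.8 | 82% |
| 20% | 10% | 46.4 v 11.6 | 66% |

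For precision, the approximate 95% half-width at 15% versus 5% is 1.96×√(0.15×0.85/232 + 0.05×0.95/116) = 6.1 points. At 10% versus 5% it is 1.96×√(0.10×0.90/232 + 0.05×0.95/116) = 5.5 points. A normal approximation would put the chance of excluding zero at about 90% and 42%; the exact 82% and 31% are the figures to use. All assume complete data and every subject in the denominator. Missing visits, or leaving out subjects at Baseline grade 3, would reduce them somewhat.

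**The case against.** A reader might infer that worsening of these signs is shut out of the AE record. The documents do not support that. Section 11.3.4 defines an AE broadly, covering any unfavourable sign that appears or worsens, and its exclusion has two exceptions. Section 11.3.4.3 adds the tolerability rule and asks sites to record AEs that staff observe. Section 12.6.1 then summarizes treatment-emergent events by arm, severity and relationship. Local harm that leads to withdrawal, or to treatment within those rules, is captured. It is also unsettled whether new pigment change is disease worsening at all: the IGA lets it coexist with clear skin, so an investigator could report it as an AE. What remains open is milder change, where recording depends on the site's reading.

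A reader might also infer that the tables would look clean whether or not harm occurred. That too goes beyond the text. If the Section 12 rule is applied to these grades, their distribution would be shown by arm, and an excess could be visible, as the 5.0-point case shows. The rule is not tied to these variables, however, and marginal counts do not identify who worsened.

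Third, Sections 12 and 12.8 defer full detail to a separate SAP. The supplied document contains no such text, so the point concerns what the protocol names. That SAP is also a natural home for the fix.

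Finally, these are unadjusted tertiary variables, and no primary or secondary result changes. That limits the weight of the point but does not remove it, because tolerability is an objective in its own right.

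**Conclusion.** The point holds in limited form. The only analysis named for the three signs cannot distinguish worsening from no change. Worsening that meets neither AE trigger has no planned subject-level tabulation by arm. The general descriptive rule offers at most marginal counts, which in the worked example shrink a 9.5-point difference in worsening to a gap of between 1.25 and 5.0 points in any-grade prevalence.

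The transition count follows from the scale alone. Every rate, and so every detection figure, is assumed. On those assumptions a direct comparison would probably detect 15% versus 5% (82%) and probably miss 10% versus 5% (31%), though it would still show the latter with its interval.

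The documents do not say that pimecrolimus or the lotion causes pigment change or dryness; Section 5 attributes dyspigmentation to corticosteroids. The point is about what the planned outputs could show, not about a known harm.

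**What to change.** Keep the tertiary endpoint. Add to Section 12.6 and the SAP, for the safety population and by treatment group:

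- a Baseline-to-visit shift table for each of the three signs at Weeks 1, 2, 4, 6 and 10;
- for each sign and visit, the number and percentage of subjects who worsened by one grade or more, among those with Baseline grade 0 to 2, with the treatment difference and its 95% CI;
- a statement that these outputs describe local tolerability, are produced whether or not an AE was recorded, use observed values (Section 12 already rules out imputing safety data), and carry no multiplicity control.

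Separately, Sections 11.3.4 and 11.3.4.3 use different triggers and must be reconciled for new or worsened pigment change and dryness, so that sites record the same event in the same way. Which trigger applies is for the sponsor to settle.

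The cost is a few descriptive tables from scores already collected, with no new visits, procedures or subjects and no change to the sample size. Three signs at five visits give 15 differences, so an isolated interval that excludes zero needs cautious reading. The tolerability picture may also come out slightly less favourable.
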